**iii. ANY KNOWN OR FORESEEABLE FACTORS THAT MAY AFFECT THE EFFECTS OR INTERPRETATION OF THE RESULTS**

The observational nature of HF and its duration can have several consequences on its outcomes. First, a high number of patients who have been lost to follow-up or died are expected.

However, replacement of patients who have been lost to follow-up or who have died is not considered due to the ambispective nature of the study.

The bias inherent in the retrospective part could also limit the quality of the data collected.

As the study is observational, factors such as age, associated comorbidities or any other confounding factors, will be taken into account during the analysis of the data.

## **E. MONITORING PLAN**

The monitoring and audit procedures described in the Good Clinical Practices will be respected.

The monitoring plan is consistent with SERF's usual practices for CI monitoring.

It includes at least one opening visit to the IC, one (or more if necessary) monitoring visits and a closing visit. All monitoring activities will be carried out and/or taken care of by SERF.

## 7. STATISTICAL CONSIDERATIONS

### A. DATA ANALYSIS

The data will be analyzed for the population as treated, since the implantation is performed prior to the start of the HF (retrospective part), in accordance with the purely descriptive nature of the objectives. The final analysis will take place when the prospective part of the HF is completed, i.e., when the last patient has been seen again during the follow-up visit and the various requests made during the monitoring activities have been closed.

### B. DATA DESCRIPTION

Demographic **data** of the included population and surgery, as well as endpoints and safety data, will be presented descriptively:

- Discrete qualitative and quantitative data will be summarized by their number, percentages, and percent confidence interval for each modality;
- Continuous quantitative data will be summarized by their mean, standard deviation, mean confidence interval, median, minimum and maximum.

**Clinical data** will be analyzed before and after surgery at each follow-up visit (functional measures) when available, including in terms of HHS and SHO-12 functional score if available, calculating score changes between preoperative and follow-up states. The confidence interval of the observed differences will make it possible to quantify the improvement or deterioration of the clinical status.

**Radiological data** will be analyzed before and after surgery at the follow-up visit. X-rays will document possible cases of complications (causal link with the bone defect), and provide information in terms of osseointegration/bone reconstruction.

Failure and revision rates will be analyzed by a Kaplan-Meier survival curve, with any revision surgery with removal or change of the SAGITTA EVL-R rod and/or locking keys as the inflection point. If several causes are identified, specific survival rates can be calculated.

The safety data related to the medical device will be presented throughout the duration of the follow-up. The complications observed can be grouped according to the data describing them provided and their etiology.

### C. ANALYTICAL PROCEDURES

#### i. CALCULATION OF CONFIDENCE INTERVALS

All confidence intervals will be calculated at 95%, i.e.:  $z_{\frac{\alpha}{2}} = 1.96$

The confidence intervals for discrete qualitative and quantitative variables will be calculated using the following formula:

$$IC_{95} = \left[ p - z_{\frac{\alpha}{2}} \times \sqrt{\frac{p \times (1-p)}{n}} ; p + z_{\frac{\alpha}{2}} \times \sqrt{\frac{p \times (1-p)}{n}} \right]$$

With:

- $IC_{95}$ , the 95% confidence interval
- p, the proportion observed;
- $z_{\frac{\alpha}{2}} = 1.96$ , the value derived from the normal distribution for a risk  $\alpha$  5%;
- n, the sample size.

The confidence intervals for the means of the continuous quantitative variables will be calculated using the following formula:

$$IC_{95} = \left[ m - z_{\frac{\alpha}{2}} \times \frac{\sigma}{\sqrt{n}} ; m + z_{\frac{\alpha}{2}} \times \frac{\sigma}{\sqrt{n}} \right]$$

With:

- $IC_{95}$ , the 95% confidence interval
- $m$ , the observed mean;
- $\sigma$ , the standard deviation observed
- $z_{\frac{\alpha}{2}} = 1.96$ , the value derived from the normal distribution for a risk  $\alpha$  5%;
- $n$ , the sample size.

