## B. EXPECTED ADVERSE REACTIONS

Known side effects (or complications) related to the use of SAGITTA® EVL R rods or the surgery required for their implantation are identified in the device's instructions for use and listed below:

- Allergy to the various materials that make up the implant and/or surgical equipment, in particular to metal,
- Pseudarthrosis, osteolysis, loosening of the prosthesis,
- Instability, dislocation, insufficient range of motion,
- Deformation, cracking or breakage of a component,
- Bone fracture,
- Collapse, migration, shortening or lengthening of the operated limb,
- Infection, sepsis,
- Delayed healing,
- Local, transient or permanent nerve damage,
- Cardiovascular disorders (hematoma, deep vein thrombosis), pulmonary embolism,
- Urinary tract infection,
- Deep abscess, fistula,
- Deterioration of the femoral and acetabular implant by stem/acetabulum contact during movements of extreme amplitude, mechanical noise may be heard when walking,
- The friction of components with each other can generate wear debris, corrosion or the release of metal particles that can induce a local reaction of the tissues,
- Residual hip pain.

*Notes:*

*Some of these complications can lead to prolonged operating time, revision surgery, or implantation failure/postponement of surgery.*

*It should be noted that any joint prosthesis is subject to wear and tear that can force the surgeon to operate again.*

*The surgeon is responsible for complications that may result from an incorrect prescription, a defective operating technique or a lack of asepsis. In no case can these complications be attributed to SERF.*

In addition, situations with an increased risk of failure are also listed:

- Severe muscular, neurological or vascular impairments affecting the affected extremity,
- Destruction, loss or poor bone quality that can affect the stability of the implant (for reasons of fatigue resistance), severe osteoporosis, significant deformities of the joint to be replaced,
- Any associated conditions that could compromise the function or implantation of the prosthesis,
- Systemic or metabolic disorders,
- Intellectual inability of patients to understand the surgeon's instructions,
- Drug addiction, alcohol, tobacco or drug abuse,
- Local bone tumors that may affect the stability of the implant,
- Obesity, overweight, high patient activities, intensive sports practices, patients with balance disorders,

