## B. EXPECTED RISKS AND ADVERSE EFFECTS THAT NEED TO BE ASSESSED

All the risks and expected adverse effects to be assessed during this CI are listed in the chapter 4.

All the complications observed will be listed in the patient's observation form.

Any effect, event, defect or malfunction that must be reported to the competent authorities will be reported in accordance with the provisions of Chapter 14.

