#### **Satisfaction**

The satisfaction of the subjects will be evaluated through a graduated scale with 5 levels (Likert scale) with the following 5 response options:

- Very satisfied,
- Rather satisfied,
- Neither satisfied nor dissatisfied,
- Rather dissatisfied,
- Very dissatisfied.

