**Radiographic evaluation:**

- *Paprosky's classification :*

This classification makes it possible to define the preoperative bone defect.

	Definition	Proximal Metaphysis	Diaphysis
I	Minimal proximal metaphyseal bone loss	Intact	Intact
II	Moderate-to-severe proximal metaphyseal bone loss	Absent	Intact
III	A Severe proximal metaphyseal bone loss with diaphysis intact for some distance	Absent	≥4 cm of isthmus
	B Severe proximal metaphyseal bone loss with diaphysis intact for some distance	Absent	< 4 cm of isthmus
IV	Complete loss of metaphyseal and diaphyseal bone	Absent	Absent

- *Preoperative fractures will be evaluated by the Vancouver Stadium^4:*

This classification of periprosthetic hip fractures proposed by Duncan and Masri is the most widely used classification system. It takes into account the site of the fracture, the condition of the femoral implant and the quality of the surrounding femoral bone material.

- **type A:** fractures involve the trochanteric area
  - **A(G):** greater trochanter
  - **A(L):** lesser trochanter
- **type B:** around the stem or just below it
  - **B1:** stem stable
  - **B2:** stem loose
  - **B3:** stem loose, bone stock inadequate
- **type C:** well below the stem

- *Osseointegration of the stem will be assessed by the Engh score (see Appendix 7)*

Measured on postoperative X-rays, it is divided into 2 subparts: fixation and stability.

The final score can be classified into 4 categories:

- $<-10^\circ$ : unstable
- $-10$  to  $<0^\circ$ : suboptimal but unstable
- $0$  to  $+10^\circ$ : suspected bone growth
- $>+10^\circ$ : osseointegration

[figure not shown]
- *Bone reconstruction will be measured by the cortico-medullary index*

This index represents the fineness of the cortex and allows us to evaluate bone quality.

$$\frac{\text{Epaisseur os cortical}}{\text{Diamètre extérieur du fémur}} \times 100$$

- *Femoral offset*

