## ii. II. CALCULATION OF THE REVISION RATE

Thus, the all-cause revision rate will be calculated as follows:

$$Taux = \frac{n}{N}$$

Where  $n$  is the number of patients who underwent revision surgery and  $N$  is the total number of patients included in HF.

Specific revision rates will be calculated using the following formula:

$$T_R = \frac{n_i}{N}$$

With:

- $n_i$ , the number of patients who required revision surgery for reason  $i$ ;
- $N$ , the sample size;

The confidence interval of each revision rate thus observed (one for each reason for revision) will also be calculated as mentioned above.

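### The Wald interval fixed for all simple proportions gives impossible lower limits and too-low upper limits at 1 to 3 events, and a zero-width interval for an empty row

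*Protocol*

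**What the plan says.** Section 7.C.i sets all intervals at 95% with z = 1.96. For proportions it states: "The confidence intervals for discrete qualitative and quantitative variables will be calculated using the following formula", and prints p ± 1.96·√(p(1−p)/n). There is no minimum count, no truncation at zero, and no exact or score alternative.

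Two other sections set its reach:

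- Section 7.B, covering demographics, surgery, endpoints and safety data: "Discrete qualitative and quantitative data will be summarized by their number, percentages, and percent confidence interval for each modality".
- Section 7.C.ii, for revision by cause: "The confidence interval of each revision rate thus observed (one for each reason for revision) will also be calculated as mentioned above".

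Some variables have a fixed list of categories. Satisfaction uses a "graduated scale with 5 levels (Likert scale) with the following 5 response options" (6.A.iii). For the Engh score, "The final score can be classified into 4 categories" (6.A.iii). Section 5.B adds: "All the risks and expected adverse effects to be assessed during this CI are listed in the chapter 4"; section 4.B gives those effects in 15 lines.

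Sections 6.C.viii and 7.E put the maximum at 120, and section 6.D.iii warns that "a high number of patients who have been lost to follow-up or died are expected". Section 3.A cites a state-of-the-art revision rate of 15.2% at 5 years.

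**The concern.** The Wald interval relies on a normal approximation that breaks down when the number of events is small. Single complications and single causes of revision in a series of this size will often have small counts. At 1 to 3 events the interval extends below zero and its upper end is too low. At zero events its width is zero.

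For a rare complication the upper limit is the informative one, because it says how frequent the event could still be. Understating it makes the device look safer than the data allow. Confirming safety from the complications observed is a stated secondary objective (5.C.ii). With no hypothesis test planned, the estimates and their intervals are what the study will report. The protocol itself fixes the formula, and section 7.K requires departures from the statistical plan to be presented and justified. An analyst who used a better interval would therefore be deviating from the plan.

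**Working it through.** **Inputs.** z = 1.96 and the Wald formula (7.C.i); n = 120 as the maximum (6.C.viii, 7.E). The protocol expects heavy loss but gives no figure, so n = 84 (30% loss) and n = 60 (50% loss) are assumptions. Event counts per row are not given, so 0 to 4 are shown.

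**Where the lower limit is negative.** With x events, p < 1.96·√(p(1−p)/n) is equivalent to 0 < x < 1.96²·n/(n + 1.96²). The bound is 3.72 at n = 120, 3.67 at n = 84 and 3.61 at n = 60. The lower limit is therefore below zero at 1, 2 and 3 events and positive from 4. Only very small subgroups differ: at n = 13, 3 events give +0.17%.

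**One case in full, 1 event in 120.** p = 0.00833 and √(p(1−p)/n) = 0.00830.

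- Wald: 0.00833 ± 1.96 × 0.00830 = −0.79% to 2.46%.
- Wilson: [p + z²/2n ± z·√(p(1−p)/n + z²/4n²)] / (1 + z²/n) = (0.02434 ± 0.02282)/1.0320 = 0.15% to 4.57%.

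The Wald upper limit is 2.46/4.57 = 54% of the Wilson one.

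**Limits in percent**

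| n | Events | Wald | Wilson |
|---|---|---|---|
| 120 | 0 | 0; 0 | 0; 3.1 |
| 120 | 1 | −0.79; 2.46 | 0.15; 4.57 |
| 120 | 2 | −0.62; 3.96 | 0.46; 5.87 |
| 120 | 3 | −0.29; 5.29 | 0.85; 7.09 |
| 120 | 4 | 0.12; 6.55 | 1.30; 8.26 |
| 84 | 0 | 0; 0 | 0; 4.4 |
| 84 | 1 | −1.1; 3.5 | 0.2; 6.4 |
| 84 | 3 | −0.4; 7.5 | 1.2; 10.0 |
| 60 | 0 | 0; 0 | 0; 6.0 |
| 60 | 1 | −1.57; 4.91 | 0.29; 8.86 |

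With no event the Wilson upper limit is z²/(n + z²); at n = 120 that is 3.8416/123.8416 = 3.1%. Clopper-Pearson is close: 3.03% for 0 and 4.56% for 1 event in 120.

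**Coverage.** Exact binomial enumeration over assumed true rates of 1% to 5%, in steps of 0.01 point:

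| | n = 120 | n = 84 | n = 60 |
|---|---|---|---|
| Wald, mean | 88.0% | 83.8% | 79.0% |
| Wald, lowest | 69.9% | 57.0% | 45.2% |
| Wilson, mean | 95.6% | 95.7% | 95.9% |
| Wilson, lowest | 92.6% | 91.6% | 91.6% |
| Wald, mean given at least 1 event | 93.9% | 95.8% | 99.3% |
| Wilson, mean given at least 1 event | 95.8% | 95.3% | 94.6% |

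At n = 120, 11.6 of the 12.0 points of Wald non-coverage are upper limits below the true rate. Given at least one event, Wald coverage at n = 120 still varies with the true rate: 99.7% at 2% and 86.0% at 4%.

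**How many rows could be sparse.** The protocol gives no frequencies. If each of the 15 lines in 4.B were a row with a true frequency of 1%, 2% or 3% (an assumption), the expected numbers are 15·P(X = 0) and 15·P(1 ≤ X ≤ 3):

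- n = 120: 4.5, 1.3 or 0.4 rows empty; 10.0, 10.4 or 7.3 rows with 1 to 3 events.
- n = 84: 6.4, 2.7 or 1.2 rows empty; 8.4, 10.9 or 10.2 rows with 1 to 3 events.

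For revisions, 0.152 × 120 = 18.2 and 0.152 × 84 = 12.8, so about 13 to 18 revisions would be divided among several causes.

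**All-cause revision, for contrast.** At a true rate of 15.2%, Wald coverage is 95.1% (n = 120) and 94.0% (n = 84). For 18 of 120, Wald gives 8.6% to 21.4% and Clopper-Pearson 9.1% to 22.7%.

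**The case against.** The strongest objection is that a zero-width interval for complications assumes a table the protocol never defines. Sections 5.B, 6.A.iii and 7.B all speak of complications that were observed. The 15 lines of 4.B come from the instructions for use, and several bundle different events. If only observed complications are tabulated, the zero row disappears for them, and with it much of the coverage shortfall: the lowest Wald figures all occur at a true rate of 1%, where they almost equal the probability of seeing any event. The relevant averages are then 93.9% to 99.3%. The row frequencies and losses are assumed, the study has no test, success criterion or stopping rule, and a negative percentage is too plainly impossible to mislead.

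Part of this stands. The 0% to 0% result arises only if an empty row is printed. It is not claimed for revision causes, since 7.C.ii covers rates actually observed. The number of sparse rows is unknown. For rows with at least one event the fault is mainly misplaced limits, with average coverage close to nominal.

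The rest does not remove the point. The limits at 1 to 3 events follow from the formula whatever the true rate is. A reader may discount a negative lower limit, but nothing in the table shows that the upper limit is too low. The sentence in 5.B on observed complications governs what is recorded in the patient's form, while the same section says the listed effects are to be assessed. A satisfaction level or Engh class can be empty in any case.

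**Conclusion.** The point holds. As written, section 7.C.i gives wrong limits for sparse proportions. At n = 120, rows with 1, 2 or 3 events have negative lower limits and upper limits about 1.8 to 2.1 points too low; at 1 event and n = 60 the shortfall is about 4 points (8.86 − 4.91). Any empty row that is tabulated gets 0% to 0% where the data allow up to 3.1% (n = 120) or 6.0% (n = 60).

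These limits depend only on the printed formula, n and the count. The smaller sample sizes, the 1% to 5% range behind the coverage figures and the number of rows affected are assumptions.

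The effect is confined to secondary descriptive and safety rows. The Kaplan-Meier primary outcome has its own estimator (7.C.iii), and the all-cause revision rate near 15% is adequately served. The formula should be corrected, but the main result is not at risk.

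**What to change.** In 7.C.i, replace the Wald formula for proportions with the Wilson 95% interval (or Clopper-Pearson), name the chosen method, and let 7.C.ii refer to it for the revision rates. Use it for all proportions, so that no switching rule by event count is needed.

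The cost is one formula and one software option; no further data, patients or visits are required. Intervals for rare events become somewhat wider and asymmetric. Wilson can fall to about 92% coverage at some true rates. Clopper-Pearson avoids that but is conservative, averaging 97.8% to 98.6% over true rates of 1% to 5% at these sample sizes.

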**viii. NUMBER OF REQUIRED TOPICS TO BE INCLUDED IN THE CI**

Over the period of implantation under consideration (01/01/2016 – 31/12/2018), 120 patients were implanted with a SAGITTA® EVL-R rod in the investigation center selected for HF and can potentially be included. Only patients who meet the screening criteria and agree to participate (inclusion) will be included and their data collected.

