### **iii. SPECIFYING SUBGROUPS FOR ANALYSIS**

Subjects can optionally be classified by assembly for analysis.

In addition, an analysis according to etiology (revision, revision with reconstruction) is envisaged. For this purpose, the CCAM codes related to the surgical procedure will be recovered.

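### The 95% interval for every mean uses 1.96 with the observed SD, so it is slightly too narrow; this matters mainly for the HHS change if few preoperative scores exist

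*Protocol*

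**What the plan says.** Section 7.C.i opens with the level, "All confidence intervals will be calculated at 95%, i.e". a multiplier of 1.96, and then writes out two formulas, one for proportions and one for means. The second is introduced by "The confidence intervals for the means of the continuous quantitative variables will be calculated using the following formula" and is m ± 1.96·σ/√n. The legend defines σ as "the standard deviation observed" and 1.96 as "the value derived from the normal distribution for a risk" of 5%. No t quantile and no small-sample alternative appears anywhere in the protocol.

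Two other places determine where this formula may meet small numbers.

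- **Score change.** Section 7.B plans changes in functional score between the preoperative and follow-up states, for patients whose scores exist, and adds: "The confidence interval of the observed differences will make it possible to quantify the improvement or deterioration of the clinical status". The schedule in section 6.A.iv takes the preoperative score from the records and excludes the SHO-12 at that time point, so in practice the change concerns the HHS.
- **Assembly.** Section 7.I.iii says: "Subjects can optionally be classified by assembly for analysis".

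On the size of the series, section 6.C.viii states that "120 patients were implanted with a SAGITTA® EVL-R rod in the investigation center selected for HF", and section 6.D.iii warns that "a high number of patients who have been lost to follow-up or died are expected".

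**The concern.** The value 1.96 is exact for a mean only when the standard deviation is known. Here it is estimated from the same patients. For normal data the standardised mean then follows Student's t with n-1 degrees of freedom, which has heavier tails. An interval built with 1.96 is therefore too short, always in the same direction, and the error grows as n falls.

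This is not a detail left to a later document: the protocol prints both the formula and its constant. Because no tests are planned (sections 7.D and 7.I.iv), the intervals are the main statement of uncertainty for means. Pain reduction and functional recovery are among the claims to be verified in section 5.A, and the HHS change bears on both. If few records hold a preoperative HHS, an interval labelled 95% would cover less than that on one of the results the sponsor most wants to show.

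**Working it through.** **Inputs.** Two-sided 95% level, multiplier 1.96, observed SD (all section 7.C.i); at most 120 patients (section 6.C.viii). Assumptions: normal data, and an SD with divisor n-1, since the protocol does not state the divisor.

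**The plan's own figure.** The 97.5% quantile of the standard normal distribution is 1.95996, which rounds to the stated 1.96. The constant itself is right; the distribution it comes from is not the one that applies.

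**Formulas.** Let t be the 97.5% quantile of Student's t with n-1 degrees of freedom.

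- Shortfall in width = 1 - 1.96/t
- True coverage of m ± 1.96·SD/√n = P(|T| < 1.96), with T distributed as t on n-1 degrees of freedom

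Example, n = 20: t = 2.093; 1 - 1.96/2.093 = 0.064, so the interval is 6.4% too narrow; coverage is 93.5%.

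| n (non-missing values or pairs) | t | Interval too narrow by | True coverage |
|---|---|---|---|
| 120 | 1.980 | 1.0% | 94.8% |
| 60 | 2.001 | 2.0% | 94.5% |
| 40 | 2.023 | 3.1% | 94.3% |
| 30 | 2.045 | 4.2% | 94.0% |
| 20 | 2.093 | 6.4% | 93.5% |
| 10 | 2.262 | 13.4% | 91.8% |

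If the SD were computed with divisor n instead, coverage would be a little lower still: 94.7% at n = 120, 93.6% at n = 30, 92.9% at n = 20 and 90.4% at n = 10.

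**Which rows may apply.** The first row is the ceiling, before any loss or death. For the HHS change, n is the number of patients with both a recorded preoperative score and a follow-up score. The synopsis and section 6.D.i describe the HHS at follow-up as additional to the centre's standard care. That makes it plausible, though not certain, that many older records lack the score. The protocol gives no count, so the rows from 60 down to 10 are a range and not a forecast.

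**The case against.** The strongest reply is that this hardly matters here. The primary outcome is a Kaplan-Meier survival rate (section 7.C.iii) and the revision rates are proportions (section 7.C.ii); neither uses the formula for means. The objectives are descriptive and there is no pass/fail criterion (section 7.G). If only 30 patients have a preoperative HHS, coverage is still 94.0%. Nor does the t interval guarantee 95%, because the HHS is bounded at 0 and 100 and its changes may be skewed. All of this stands, and it limits the weight of the point. It does not make the formula right: for normal data the t quantile is exact at every n, and it converges to 1.96 as n grows.

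Two stronger readings are tempting and should be set aside.

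- A reader might divide 120 stems by the 28 catalogue references in section 2.C, get about 4 per group, and conclude that coverage falls to about 86%. The protocol never equates an assembly with a catalogue reference. The 28 references count left and right versions separately, and the schedule in section 6.A.iv lists implant type and assembly side by side. Section 6.A.iii applies assemblies to survival rates, and the classification in section 7.I.iii is optional and names no variable. A split by the three stem lengths would, if equal, give 120/3 = 40 per group and 94.3% coverage.
- A reader might also infer that the interval settles whether patients improved. Section 7.B says only that it serves to quantify the change; no decision rule is attached.

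**Conclusion.** The point holds as a minor correction. The stated interval for means is too narrow at every n, because a normal multiplier is paired with an estimated SD and no small-sample rule is given. For the full series the effect is negligible: about 1% of width and 0.2 percentage points of coverage. It becomes noticeable at roughly 20 to 30 values or fewer, with coverage of 94.0% at n = 30, 93.5% at n = 20 and 91.8% at n = 10.

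The firmest case is the HHS change, because it depends on what the old records contain, in a series where heavy loss is expected. Means by assembly are a weaker case, since they are optional. The size of the error in either set rests on an n that the protocol does not state, and the coverage figures assume normal data. The primary outcome is not affected.

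**What to change.** In the second formula of section 7.C.i, replace 1.96 by the 97.5% quantile of Student's t with n-1 degrees of freedom. Define n as the number of non-missing values in the group shown, or the number of complete pairs for a change from the preoperative state, and report n beside each interval. Limit the opening statement that sets 1.96 for all intervals accordingly, so that it no longer covers means. The formula for proportions is a separate matter.

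The cost is one symbol and a line of definition. No further data are needed. Intervals based on few values become wider, by 15.4% at n = 10 (2.262/1.96 = 1.154) and 4.3% at n = 30 (2.045/1.96 = 1.043), while those on the full series are practically unchanged. It is best done before the analysis, because section 7.K requires any later departure from the stated formula to be reported and justified as a deviation.
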